### **7.3. HIPAA Authorization**

Prior to patient participation in the study, written informed consent will be obtained from each patient (or the patient's legally accepted representative) according to ICH GCP and to the regulatory and legal requirements of MHS. Each signature must be personally dated by each signatory and the informed consent and any additional patient information form retained by the investigator as part of the study records. A signed copy of the informed consent and any additional patient information must be given to each patient or the patient's legally accepted representative.

The patient must be informed that his/her personal study-related data will be used by the Principal Investigator in accordance with the local data protection law. The level of disclosure must also be explained to the patient.

The patient must be informed that his/her medical records may be examined by authorized monitors or Clinical Quality Assurance auditors appointed by appropriate IRB members, and by inspectors from regulatory authorities.

### **7.4. Withdrawal**

Patients will have originally consented to trial follow-up procedures, including chest x-ray, CT scan, and blood tests where appropriate. Patients have the right to withdraw from the trial at any point. A request by a patient to withdraw does not have to be justified and will not affect future or ongoing care. In the event of withdrawal, any details available regarding the reason(s) will be recorded. Data the patient has previously consented for us to collect and analyses will be retained but no further data will be collected. Patients who withdraw before randomization will not be included in the final analysis. Because the only investigational intervention in this protocol occurs immediately following enrollment, any patient who withdraws from the study, either at their own request or at the investigator's discretion, will be offered all scheduled follow-up care or imaging as detailed in the protocol, as this is considered optimal care for a patient after pleurodesis.

[figure not shown]
## 8. PROCEDURES

Figure 1 shows the proposed workflow through the trial. Following the informed consent, each participant is assigned a unique study number and baseline data will be collected before randomization. At this point the research nurse will briefly explain the procedure and familiarize the participant with the Visual Analogue Scale (VAS) system for dyspnea (Appendix I) and pain (Appendix II). Trial treatment will be delivered by means of either a pigtail chest tube (size 10-14 Fr) or PleurX® catheter at bedside after randomization. Outcome measures will be assessed daily until the chest tube is removed and at routine follow-up visits at approximately 14 days, 28 days and three months after the day of procedure as outpatients if the patient has been discharged. While the chest tube is in place, daily symptom assessment will be performed, and daily chest x-ray (PA and lateral when possible) and 24-hour drain output will be recorded (Appendix III) to determine if RSP has been achieved, or if further intervention is indicated.

RSP is defined as chest tube drainage less than 100 cc over the previous 24 hours and a chest x-ray showing similar or decreased pleural space opacification compared to the baseline chest x-ray done the day of pleurodesis (day 0).

Objective determination of the chest x-ray finding will be based on the formal Radiology report in the medical record. If necessary, the findings will be clarified by personal communication between study personnel and the Radiologist reading the film. The algorithm for chest tube and pleural space management after TSP is specified in Figure 2. If RSP is not achieved on day 3, then management will be determined using the algorithm based on the chest x-ray findings and pleural drainage, and may include continued observation, repeat cathflo activase, chest CT, insertion of additional pleural drainage tubes, and repeat TSP with or without cathflo activase. At all follow-up visits after the chest tube has been removed, assessment will include chest x-ray and completion of the VAS for pain and dyspnea.

[figure not shown]
Figure 1. Proposed Workflow of the Trial

Assessments/tasks at visits:

- ◆ VAS scores for pain and SOB
- ◆ Drained volumes in 24 hours if the chest tube is still in place
- ◆ Serum hemoglobin if the chest tube is place
- ◆ CxR (PA and lateral)
- ◆ CT scan, as justified by the PI

Figure 2: Chest Tube Management Algorithm

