## 5.0. STUDY DESIGN

The SPIRIT (Standard Protocol Items for Randomized Trials) recommendations were followed in preparing this protocol.(20,21) The study is a single center, prospective, randomized, double-blind, placebo-controlled trial with two arms to compare the successful pleurodesis rates and potential complications after TSP with or without cathflo activase in patients with recurrent pleural effusion.

This study is designed as a single center study at MHS with two study sites, although it may be made available to thoracic surgery programs at other institutions to consider opening as a collaborative effort to accelerate patient accrual. All patients for whom bedside chemical pleurodesis is planned will be considered eligible for the study regardless of effusion etiology. Chest X-ray and chest tube insertion will be performed in all consented participants, and the drained pleural fluid amounts will be recorded and, if not done before enrollment, sent for chemical, bacteriological and cytological evaluation. Then the participants will undergo stratified randomization according to effusion etiology (malignant vs. non-malignant) with the use of a computer-based system in a 1:1 ratio. TSP with cathflo activase or placebo will be administered through the chest tube immediately after randomization. The trial will be conducted on a double-

blind basis and therefore participants and the clinician will be unaware of each participant's allocated treatment group.

Additional centers may be invited to participate, in which case the IRB will be notified if other programs decide to open the protocol at other sites.

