### **6.2. Inclusion and Exclusion Criteria**

All patients for whom bedside chemical pleurodesis is planned will be considered eligible for the study regardless of effusion etiology. The experience to date has been that there is no relative or absolute contraindication to the use of cathflo activase with pleurodesis, including patients with bloody pleural effusion. The principal investigator or a nominated member of the research team will approach participants who fulfill the criteria for inclusion in the trial.

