#### **6.2.1. Inclusion Criteria**

1. Age > 18 years
2. Symptomatic pleural effusion requiring intervention
3. Expected survival > 3 months
4. Written informed consent to trial participation

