## 8.3. Treatments/Interventions

The trial interventions are summarized in Figures 1 and 2 and described in detail below. The delivery of each of the treatment and its aftercare will be provided according to its usual practice protocols and are not specified in this trial. All patients will have a pigtail chest tube (size 10-14) inserted under image guidance, or PleurX® catheter placement. This is current practice for management of these patients. Prior to pleurodesis the chest tube will be managed to achieve the most complete fluid drainage possible as assessed by CxR and determined by the clinical team. In the case of uncertainty, chest CT will be used to confirm the drainage of fluid and adequate inflation of the lung.

For all subjects, talc slurry (sterile talc, 5 gm, mixed with lidocaine, 20 mg, diluted in sterile saline to a total volume of 100 mL and dispensed into two 60 mL luer lock syringes, prepared by MHS Pharmacy Department) will be instilled through the chest tube at bedside. This will be followed immediately by instillation of either placebo (arm 1: 50 mL normal saline) or study drug (arm 2: cathflo activase, 4 mg, suspended in 50 mL normal saline). This syringe will be prepared by the MHS Pharmacy Department based on the randomization results and coded so that neither the administering clinical team nor the patient will be able to discern to which arm the patient has been assigned. The chest tube will be clamped with orders written to unclamp in 12 hours and insure

the tube is connected to a pleural drainage system (e.g. Pleurevac®) set for standard suction of -20 cm H2O. Daily assessments will be performed until the chest tube is removed. These include drainage volume over 24 hours, CxR, and pain and dyspnea scores.

Drainage volume over the prior 24 hours will be recorded daily using the Bedside Pleural Drainage Record. If the volume is less than 100 cc/24 hours for day 3 (defined as the third 24-hour period following TSP) and the CxR on day 3 shows the pleural space is the same or better than baseline, then the chest tube will be removed. If the chest tube is not removed, management will be according to the algorithm in Figure 2, and may include: continued monitoring, chest CT to evaluate for residual loculated effusion, cathflo activase to evacuate undrained effusion, or repeat TSP with or without cathflo activase.

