## **9.0 STATISTICAL METHODS**

### **9.1. Primary and Secondary Outcome measures**

The primary outcome measure is the proportion of patients with successful pleurodesis at day 3 after administration of TSP. Successful pleurodesis is defined as “radiographically satisfactory pleurodesis” (RSP), as evidenced by 1) chest x-ray demonstrating similar or decreased amount of pleural fluid/opacification compared to day 0 (day pleurodesis is performed) and 2) drainage

of less than 100 ml of fluid over the preceding 24 hours. Chest x-ray results will be scored on a three-point scale (-1, 0, +1) based on comparison of pleural space opacification on the side of the TSP to baseline:

1. Worse (-1): Pleural space opacification is worse, suggesting residual undrained fluid or reaccumulation of loculated fluid.
2. Same (0): Pleural space opacification similar to baseline.
3. Better (+1): Pleural space opacification is better, suggesting less pleural fluid than at baseline.

The secondary outcome measures will include the following:

1. Proportion of patients with RSP at any time after TSP
2. Duration of chest tube drainage
3. Days to achieve RSP
4. Pain and dyspnea scores as assessed by a visual-analogue scale (on a scale from 0 to 100 mm, with a score of 0 indicating a complete absence of symptoms and a score of 100 maximum symptoms).
5. Proportion of patients requiring repeat pleurodesis
6. Proportion of patients requiring additional chest tube
7. Change in serum hemoglobin levels within three days of cathflo activase
8. Length of hospital stay (in days) after TSP.
9. All hospital costs associated with both treatment arms.

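### Day-3 RSP requires no change from the pre-TSP state, and pre-TSP tube output is neither in the baseline list nor used in the analysis, so the arm difference may be attenuated by an unknown amount

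*Combined protocol and SAP*

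**What the plan says.** **Endpoint.** Section 8 gives the definition: "RSP is defined as chest tube drainage less than 100 cc over the previous 24 hours and a chest x-ray showing similar or decreased" opacification against the film from the day of pleurodesis. Section 9.1 scores the film on three levels, and the middle one, "Same (0): Pleural space opacification similar to baseline", counts towards success. The drainage half is an absolute level in one 24-hour period. Section 8.3 fixes the time: "If the volume is less than 100 cc/24 hours for day 3 (defined as the third 24-hour period following TSP").

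**Entry.** Section 6.2 is broad: "All patients for whom bedside chemical pleurodesis is planned will be considered eligible for the study regardless of effusion etiology". The only criterion on the effusion itself in 6.2.1 is "Symptomatic pleural effusion requiring intervention". No minimum volume or output is set.

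**State at baseline.** Section 8.3: "Prior to pleurodesis the chest tube will be managed to achieve the most complete fluid drainage possible as assessed by CxR". The reference film therefore shows a chest that has already been drained.

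**Data and analysis.** Section 5.0 says that, around tube insertion and before randomisation, "the drained pleural fluid amounts will be recorded", but not as a 24-hour rate. The eight items in the 8.2 pre-randomisation list do not include tube output; it appears only in the list for visits after TSP. Randomisation is stratified by etiology alone (6.3). The primary test in 9.2 is a chi-square with no covariate.

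**The concern.** A patient draining 70 mL/24 h before TSP and 80 mL on day 3, with an unchanged film, is scored as a successful pleurodesis. The two values do not show how much of that result was the patient's starting state. If many patients start under the threshold, part of the RSP rate in both arms reflects low starting output, and the difference between arms may have to come largely from the remaining patients.

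Two things are at stake. One is sensitivity: a real effect could be harder to see. The other is interpretation: an absolute RSP rate of, say, 60% cannot be read as the rate at which talc produced pleurodesis unless the reader knows how many patients were already under 100 mL/24 h. A value measured before randomisation would address both, and the plan neither lists it nor uses it.

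**Working it through.** **1. Reproduce the sample size.** Inputs from 6.1: 60% versus 80%, one-sided 5%, 80% power, 5% loss. With pooled variance under the null and no continuity correction:

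n = [1.645·√(2·0.7·0.3) + 0.842·√(0.6·0.4 + 0.8·0.2)]² / 0.2² = (1.066 + 0.532)² / 0.04 ≈ 63.9, so 64 per arm.

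64 / 0.95 = 67.4, so 68 per arm and 136 in total. This matches the plan. Power with 64 evaluable per arm is 80.1%.

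**2. Possible attenuation.** Let f be the share of patients already under 100 mL/24 h before TSP. The documents do not give f, so the values below are assumptions.

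*Reading A:* 60%/80% hold only for the other patients, and the share f succeeds in both arms whatever the treatment. The arm rates are f + (1−f)·0.6 and f + (1−f)·0.8, and the difference is 0.2·(1−f).

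| f | RSP rates | Difference | Power, 64 per arm |
|---|---|---|---|
| 0 | 60% vs 80% | 20 points | 80.1% |
| 10% | 64% vs 82% | 18 points | 74.6% |
| 20% | 68% vs 84% | 16 points | 68.5% |
| 30% | 72% vs 86% | 14 points | 61.9% |

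If the share f succeeds in only 70% of cases, equally in both arms, power is 72.2%, 63.1% and 53.4% for f = 10%, 20% and 30%. Both versions assume no benefit at all in that group.

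*Reading B:* 60%/80% are overall RSP rates that already include such patients. Power stays at 80.1% for any f. With f = 20%, the implied contrast in the rest is (0.6−0.2)/0.8 = 50% versus (0.8−0.2)/0.8 = 75%.

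**3. How often would RSP occur with no effect of anything?** Assumed model: lognormal output, between-patient log SD 0.8, day-to-day log SD 0.3 to 0.5, film read as same or better in 80% to 95%, 400,000 simulated patients per scenario.

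| Assumed median pre-TSP output | RSP with no effect |
|---|---|
| 100 mL/24 h | 40–48% |
| 150 mL/24 h | 25–32% |
| 250 mL/24 h | 11–16% |
| 400 mL/24 h | 4–7% |

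Among patients at or above 100 mL before TSP, the no-effect rate is 4–16% (medians 150–250 mL). Among those already under 100 mL, 26–56% fail day-3 RSP at the same medians (20–64% over all scenarios). A low starting output is therefore not a guaranteed success.

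**4. What adjustment would gain.** Simulated with a latent normal day-3 result calibrated to 60%/80%, 64 per arm, one-sided 5%: unadjusted test versus the likelihood-ratio test for arm in a logistic model with pre-TSP output as covariate.

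| Assumed correlation of pre-TSP output with the latent day-3 result | Unadjusted | Adjusted |
|---|---|---|
| 0 | about 81% | about 81% |
| 0.3 | about 81% | about 82–83% |
| 0.5 | about 81% | about 86% |
| 0.7 | about 81% | about 91% |

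The simulated unadjusted power is slightly above the 80.1% from the formula.

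**The case against.** The case for leaving the plan alone has several sound parts.

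- **Timing.** A reader might infer that some patients have succeeded before treatment. They have not: RSP is scored only on day 3, and a patient with low output can still fail through later output or a worse film. Such patients also have room to benefit, since section 3.1 describes loculations forming several days after pleurodesis. This stands, and it makes reading A an extreme.
- **Sample size.** A reader might infer that 136 is too few. Section 6.1 states both planning rates as RSP rates and cites the centre's own experience. If that population had a similar mix, reading B applies and planned power is intact. This stands.
- **Validity.** A reader might infer that the research question in 3.3 cannot be answered. It asks about the addition to talc slurry against talc slurry alone, and the concurrent randomised talc arm answers that without pre-TSP output. Attenuation falls on both arms alike and does not inflate type I error. This stands.
- **Film criterion.** After maximal drainage, not getting worse is a reasonable target. Draining the space also does not establish that fluid production is low. Both remarks stand, and they are reasons to keep RSP as it is.
- **Material not shown.** Appendices III and IV may capture pre-TSP output. The gap is established only for the 8.2 list and the 9.2 analysis.

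These points limit the harm but do not remove the gap. The value that would show how large f is, and that could sharpen the comparison, is not in the prespecified baseline list and has no role in the analysis.

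**Conclusion.** The point holds in a limited form. RSP needs no change from the pre-TSP state, nothing at entry excludes patients already under 100 mL/24 h, and this may attenuate the arm difference. The amount is unknown because the documents give no pre-TSP output. Under the assumed shares of 10% to 30% in reading A with sure success, the difference would be 18 to 14 points instead of 20; under reading B planned power does not change. The documents do not say which reading applies.

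They do not support the stronger conclusions that the randomised comparison is biased, that its error rate is inflated, or that the sample size is wrong. What remains is an inexpensive improvement in precision and interpretability. It is worth making before enrolment, because an uncollected baseline value may not be recoverable and an adjustment chosen after unblinding would carry little weight. The gain of roughly 0 to 11 points of power rests on an assumed correlation of 0 to 0.7.

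**What to change.** Keep the RSP definition, eligibility and sample size.

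1. **Section 8.2, pre-randomisation list:** add tube output in the last 24 hours before TSP, with the hours of drainage it covers. Where the tube has been in for less than 24 hours, scale the volume or flag it by a stated rule.
2. **Section 9.2, primary test:** replace the unadjusted chi-square with a prespecified comparison of day-3 RSP adjusted for etiology (the stratification factor) and pre-TSP output. One option is logistic regression, testing the arm term and reporting a standardised risk difference. Enter output as log(output + 1), or another transform defined at 0 mL. State how missing baseline values are handled, and use the same test at the interim look. Keep the chi-square as a sensitivity analysis.
3. **Reporting:** give by arm the number of patients under 100 mL/24 h before TSP, and day-3 RSP among those at or above 100 mL as a supportive, not key, analysis. The split uses a pre-randomisation value, so the comparison within it remains fair.
4. **Section 6.1:** state whether the 60% came from patients with similar pre-TSP output.

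The cost is one field and a paragraph in 9.2. Section 5.0 already has drained amounts recorded, though not as a 24-hour rate, so some values will be missing or scaled. The supportive subset will be smaller than the trial. If pre-TSP output turns out not to predict day-3 RSP, power is about what it was.

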### 8.1. Study Duration and Timeline

This is an 18-month trial with a minimum of three months of follow-up and subsequent data analysis and manuscript production. Enrolment will start in January 2020 and is anticipated to continue until July 2021. Patient data will be anonymized with trial number allocations. Data will be collected and managed using REDCap electronic data capture tools hosted at Office of Human Research of MHS.

## 8.2. Assessments/Tasks

Following consent, a baseline assessment will be undertaken pre-randomization by a member of the trial team and entered into the REDCap system hosted at Office of Human Research of MHS. The following data will be recorded prior to randomization:

1. Patient demographics and physical characteristics
2. Mode of presentation, current diagnosis, cause of effusions (if known).
3. Medical history and current medication.
4. Previous pleural interventions.
5. Symptoms, including pain and SOB according to a visual analog scale (VAS) (Appendix I, II).
6. Pleural fluid biochemical and cytological test results
7. Baseline hemoglobin (day of or day before TSP)
8. Baseline (day of or day before TSP) CxR and chest CT (if available) findings.

After randomization and TSP with or without cathflo activase, all patients will have daily follow-up until the chest tube is removed, and at 14 and 28 days, and three months after TSP. At all visits, the following data will be recorded:

1. VAS for chest pain and SOB will be documented (Appendix I, II).
2. CxR (PA and lateral preferred).
3. Drained pleural volumes in 24 hours (if the chest tube is still in place).
4. Serum hemoglobin (only for inpatient visits within three days of the pleurodesis procedure).
5. Repeat pleural interventions.
6. Chest CT scan, as justified by the principal investigator.

## 8.3. Treatments/Interventions

The trial interventions are summarized in Figures 1 and 2 and described in detail below. The delivery of each of the treatment and its aftercare will be provided according to its usual practice protocols and are not specified in this trial. All patients will have a pigtail chest tube (size 10-14) inserted under image guidance, or PleurX® catheter placement. This is current practice for management of these patients. Prior to pleurodesis the chest tube will be managed to achieve the most complete fluid drainage possible as assessed by CxR and determined by the clinical team. In the case of uncertainty, chest CT will be used to confirm the drainage of fluid and adequate inflation of the lung.

For all subjects, talc slurry (sterile talc, 5 gm, mixed with lidocaine, 20 mg, diluted in sterile saline to a total volume of 100 mL and dispensed into two 60 mL luer lock syringes, prepared by MHS Pharmacy Department) will be instilled through the chest tube at bedside. This will be followed immediately by instillation of either placebo (arm 1: 50 mL normal saline) or study drug (arm 2: cathflo activase, 4 mg, suspended in 50 mL normal saline). This syringe will be prepared by the MHS Pharmacy Department based on the randomization results and coded so that neither the administering clinical team nor the patient will be able to discern to which arm the patient has been assigned. The chest tube will be clamped with orders written to unclamp in 12 hours and insure

the tube is connected to a pleural drainage system (e.g. Pleurevac®) set for standard suction of -20 cm H2O. Daily assessments will be performed until the chest tube is removed. These include drainage volume over 24 hours, CxR, and pain and dyspnea scores.

Drainage volume over the prior 24 hours will be recorded daily using the Bedside Pleural Drainage Record. If the volume is less than 100 cc/24 hours for day 3 (defined as the third 24-hour period following TSP) and the CxR on day 3 shows the pleural space is the same or better than baseline, then the chest tube will be removed. If the chest tube is not removed, management will be according to the algorithm in Figure 2, and may include: continued monitoring, chest CT to evaluate for residual loculated effusion, cathflo activase to evacuate undrained effusion, or repeat TSP with or without cathflo activase.

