## 9.2. Statistical Analysis Plan

Statistical summaries and analyses of data will be performed at MHS. Descriptive analysis will be performed for all data including means and standard derivation or medians for continuous variables and proportions for categorical variables. Comparison of outcomes between the two arms will be performed using t-test for numerical variables and Pearson  $\chi^2$ -test or Fisher's exact for categorical variables, and a one-sided p-value of 0.05 will be considered to be statistically significant.

The main analysis for primary outcome will be performed as per the intention-to-treat principle, and will include all the randomized participants with an observed outcome.(26) The primary outcome of the success rate of pleurodesis at day 3 will be analyzed using  $\chi^2$ -test. Time to symptomatic fluid recurrence following initial successful pleurodesis within 3 months follow-up period will be analyzed using a log-rank test. An interim analysis will be performed by the Memorial Healthcare System Quality and Safety Steering committee under [name] (currently officially the DSMB for MHS) after 50 patients are randomized in order to test for efficacy. The O'Brien-Fleming stopping rule will be used, which requires a P value of < 0.0088 (1-sided) for the primary outcome in order to stop at the interim analysis. The O'Brien-Fleming rule requires a P value of < 0.05 (1-sided) at the final analysis in order to declare a statistically significant difference in the primary outcome.(27) Analyses will be performed with the use of Prism 7.0 or SPSS 26 software.

Costs will be those related to study medications, initial hospital stay, and subsequent hospitalizations. All costs will be reported in US dollars and in 2020 prices. Cost data for both

arms will be obtained from MHS Strategic Financial Support Services. Outcomes will be measured in terms of probability of treatment success and/or complication, and utility of health states, which will be transformed to quality-adjusted life years (QALYs), calculated as the success rate of pleurodesis from each patient at day 3 after administration of TSP combined with pain and dyspnea scores.

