### **11.3. Potential Benefits to Subjects**

There may be an immediate potential benefit to patients. The combination of talc with cathflo activase may increase successful pleurodesis rates and may also shorten the time of pleurodesis compared to talc alone, thus potentially improving patient symptoms and reducing the need for additional pleural interventions and hospital stay. Patient discomfort may also be reduced by earlier chest tube removal and shorter pleurodesis times.

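### Pain and dyspnea VAS have no named analysis time, and from about day 4 to day 13 only day-3 failures are scored, so the generic t-test can become a comparison of subsets selected after randomisation

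*Combined protocol and SAP*

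**What the plan says.** **Collection.** Section 8.3: "Daily assessments will be performed until the chest tube is removed. These include drainage volume over 24 hours, CxR, and pain and dyspnea scores". Section 8.2 sets the wider schedule: "all patients will have daily follow-up until the chest tube is removed, and at 14 and 28 days, and three months after TSP". Section 8 confirms that scoring resumes after removal: "At all follow-up visits after the chest tube has been removed, assessment will include chest x-ray and completion of the VAS for pain and dyspnea". Section 8.2 also has pain and dyspnea VAS recorded before randomisation.

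**Tube removal.** Section 8.3 removes the tube if day-3 drainage is below 100 cc in 24 hours "and the CxR on day 3 shows the pleural space is the same or better than baseline, then the chest tube will be removed". These are the two components of RSP, and section 9.1 makes RSP the endpoint: "The primary outcome measure is the proportion of patients with successful pleurodesis at day 3 after administration of TSP".

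**Analysis.** Section 9.1 lists "Pain and dyspnea scores as assessed by a visual-analogue scale" as a secondary outcome on a 0 to 100 mm scale, with no time point, change score or summary. Section 9.2 says "Comparison of outcomes between the two arms will be performed using t-test for numerical variables". It gives no repeated-measures model and no rule for scores that are absent because the tube is out. Its intention-to-treat statement covers the primary outcome only.

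**The concern.** Whether a patient is scored daily after day 3 is decided by the primary endpoint, which the treatment is expected to change. In that window the scored patients are a post-randomisation subset, of different size and possibly different severity in each arm. Under section 8.3 they may also have had further cathflo activase or repeat TSP by then.

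Because no time point is named, nothing stops the analyst from testing a day in that window, or from averaging every daily score a patient has. The first compares failures with failures. The second compares three-day averages with longer ones, mixed in different proportions by arm.

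Secondary hypotheses 6 and 7 and secondary objectives 9 and 10 rest on these scores. Section 9.2 also feeds pain and dyspnea scores into the QALY calculation, again without a time point.

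**Working it through.** **Inputs from the documents.** Day-3 RSP of 60% (control) and 80% (cathflo), 68 per arm, one-sided 5%, 80% power, 5% loss (section 6.1); the schedule and removal rule (sections 8, 8.2, 8.3). The documents give no VAS course, SD, tube duration in failures or correlation with RSP. Values for these below are assumptions.

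**1. The plan's own figure.** n per arm = [1.645 × √(2 × 0.7 × 0.3) + 0.842 × √(0.6 × 0.4 + 0.8 × 0.2)]² / 0.2² = 63.9, so 64. Then 64 / 0.95 = 67.4, so 68 per arm and 136 in total. This matches section 6.1. There is no VAS calculation to reproduce.

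**2. Who has a scheduled score** (before ordinary dropout)

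| Time | Control | Cathflo |
|---|---|---|
| Days 1 to 3 | 68 | 68 |
| Days 4 to 13 | at most 68 × 0.40 = 27.2 | at most 68 × 0.20 = 13.6 |
| Days 14, 28, three months | 68 | 68 |

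In the middle row 40.8 of 136 (30%) can be scored, and 95.2 (70%) have nothing scheduled. With 64 per arm it is about 26 against 13.

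**3. A t-test within days 4 to 13.**
- Precision: the standard error of the arm difference is √(1/27.2 + 1/13.6) = 0.332 SD, against √(2/68) = 0.171 SD with everyone scored, a ratio of 1.94.
- Bias: assume the drug has no effect on VAS, failures are the worst 40% and worst 20% on a normal severity scale, and severity correlates rho with VAS. The mean of the worst fraction q is φ(z)/q, where z is the 1 − q quantile. This gives 0.966 for q = 0.4 and 1.400 for q = 0.2. The false difference against cathflo is rho × (1.400 − 0.966): 0 at rho 0, 0.13 SD at 0.3, 0.22 SD at 0.5, 0.30 SD at 0.7 and 0.43 SD at 1.

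**4. A t-test on each patient's mean of all daily scores.** Assume the same course in both arms: 50 mm on day 1, falling 5 mm/day to a floor of 20 mm. Successes average days 1 to 3: (50 + 45 + 40)/3 = 45 mm. Failures average m over a longer stay. The arm difference is (0.8 × 45 + 0.2 × m) − (0.6 × 45 + 0.4 × m) = 0.2 × (45 − m).

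| Failures keep tube to | m (mm) | False excess with cathflo (mm) |
|---|---|---|
| Day 5 | 40.0 | 1.0 |
| Day 7 | 35.0 | 2.0 |
| Day 10 | 30.5 | 2.9 |

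With a flat course the excess is 0. With a fall of 2.5 mm/day and stay to day 7 it is 0.2 × (47.5 − 42.5) = 1.0 mm. With the 5 mm/day course and assumed SDs of 15 mm between and 10 mm within patients, simulation of 4,000 trials gave one-sided 5% rejection for more pain of about 10%, 18% and 25% in the three rows. The same test on days 1 to 3 alone rejected 5 to 6% of the time.

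**5. A possible change of sign.** Further assume that removal lowers pain by 15 mm and failures keep the tube to day 7. Successes gain on days 4 to 7, so the true day 1 to 7 difference is −0.2 × 15 × 4/7 = −1.7 mm (favouring cathflo). The recorded means still show +2.0 mm, because the gain falls where successes are not scored.

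**The case against.** A reader might infer that every score after day 3 comes from failures, and that the planned t-test therefore does not compare the randomised arms. The documents do not support either statement. Sections 8 and 8.2 schedule VAS for all patients at 14 days, 28 days and three months, and a t-test there, or on days 1 to 3, is a randomised comparison apart from ordinary dropout. Nothing in section 9.2 says the test will use days 4 to 13 or an average of daily scores. The mean of all daily scores is an assumed summary, chosen to show what the wording permits.

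The size of the bias is also assumed. It depends on the slope, vanishes with a flat course, and stays below 3 mm on a 100 mm scale in the cases shown. The change of sign needs both that summary and the assumed 15 mm fall.

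Hypothesis 6 concerns pain associated with TSP, for which days 1 to 3 are directly relevant and fully scored. The statement in section 11.3, "Patient discomfort may also be reduced by earlier chest tube removal and shorter pleurodesis times", is a hedged potential benefit and not an objective, so leaving it unmeasured is not in itself an analysis defect. Figures 1 and 2 are not shown, and the drainage record and study datasheet (Appendices III and IV) are not in the text. They might fix recording times.

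All of this stands and limits the point. It does not remove the gap: the current wording permits both valid and invalid comparisons and does not choose between them.

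**Conclusion.** The defect is an unspecified VAS time point or summary combined with outcome-dependent collection between about day 4 and day 13. At the planning rates, at most about 27 of 68 control and 14 of 68 cathflo patients contribute in that window. These counts follow from sections 6.1 and 8.3, taking all tubes to be in place through day 3.

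The millimetre, SD and rejection figures are illustrations under stated assumptions and do not predict this trial's bias. They show that it can range from nothing to enough to raise a nominal 5% error rate to about 25%. The VAS is a secondary outcome and the primary analysis is unaffected, so this should be corrected but does not threaten the main result.

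**What to change.** - **Sections 9.1 and 9.2:** limit the between-arm VAS comparison to days 1, 2, 3, 14, 28 and three months, and state which of these contrasts answers hypotheses 6 and 7 and objectives 9 and 10.
- **Model:** replace the unadjusted t-test with one repeated-measures model per scale, with arm, time and their interaction, adjusted for the baseline VAS already collected. State how ordinary missing visits are handled.
- **Days 4 to 13:** report descriptively only, with the number scored in each arm.
- **QALY calculation:** name the VAS times it uses, from the same list.
- **Optional:** if the sponsor wants evidence on comfort after earlier removal, score VAS daily to one fixed day in all patients whatever the tube status. The tube-removal rule itself is not touched.

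The main change costs wording only. The optional one adds a few VAS entries per successful patient.
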